2. OBJECTIVES, ENDPOINTS, AND HYPOTHESIS

2.1. Objectives and Endpoints

2.1.1. Objectives

Primary Objective

- To compare the overall response rate (ORR) in subjects treated with daratumumab in combination with atezolizumab versus atezolizumab alone.

Secondary Objectives

- To assess the safety of the combination of daratumumab and atezolizumab
- To compare the duration of response (DoR) in subjects treated with daratumumab in combination with atezolizumab versus atezolizumab alone
- To compare the clinical benefit rate (CBR) in subjects treated with daratumumab in combination with atezolizumab versus atezolizumab alone
- To compare progression-free survival (PFS) in subjects treated with daratumumab in combination with atezolizumab versus atezolizumab alone
- To compare overall survival (OS) in subjects treated with daratumumab in combination with atezolizumab versus atezolizumab alone
- To evaluate the pharmacokinetic and immunogenicity profile of daratumumab when given in combination with atezolizumab
- To evaluate the pharmacokinetic and immunogenicity profile of atezolizumab when given in combination with daratumumab.

Exploratory Objectives

- To compare ORR evaluated by the Immune-Related Response Evaluation Criteria in Solid Tumors (irRECIST)
- To explore biomarkers predictive of response to therapy
- To evaluate potential pharmacodynamic biomarkers in response to therapy
- To explore the relationships between pharmacokinetics, pharmacodynamics, adverse event profiles, and clinical activity of daratumumab given in combination with atezolizumab in subjects with previously treated advanced or metastatic NSCLC
- To explore the benefit of daratumumab and atezolizumab treatment in subjects who had confirmed disease progression on atezolizumab monotherapy.

2.1.2. Endpoints

Primary Endpoint

- The primary endpoint is ORR: the proportion of subjects with a partial response (PR) or complete response (CR) as defined by RECIST 1.1

Secondary Endpoints

- Incidence of adverse events
- DoR: the duration from the date of the initial documentation of a response to the date of the first objectively documented evidence of recurrence or progressive disease or death, whichever status is recorded first.
- CBR: the proportion of subjects who achieve disease control (CR, PR, or SD with duration of at least 16 weeks).
- PFS: the duration from the date of randomization to the date of objectively documented progression or death due to any cause, whichever status is recorded first.
- OS: the duration from the date of randomization to the date of death due to any cause.
- Serum daratumumab concentration (C_{min} , C_{max}) and incidence of anti-daratumumab antibodies
- Serum atezolizumab concentration (C_{min} , C_{max}) and incidence of anti-atezolizumab antibodies

Exploratory Endpoints

- ORR_i: the proportion of subjects with a partial response (PR) or complete response (CR) evaluated by irRECIST
- ORR, DoR, CBR, incidence of adverse events, daratumumab and atezolizumab serum concentration and incidence of anti-daratumumab antibodies and anti-atezolizumab antibodies

Refer to Section 9, Study Evaluations for evaluations related to endpoints.

2.2. Hypothesis

The primary hypothesis is that daratumumab in combination with atezolizumab will significantly improve ORR compared to atezolizumab alone in subjects with NSCLC.

3. STUDY DESIGN AND RATIONALE

3.1. Overview of Study Design

This is a randomized, open-label, parallel-group, multicenter Phase 1b/2 study assessing the anti-tumor activity and safety of daratumumab in combination with atezolizumab compared with atezolizumab alone in subjects with previously treated advanced or metastatic NSCLC. Approximately 96 subjects will be enrolled in this study, including 6 subjects in a safety run-in cohort followed by 90 subjects randomly assigned in a 1:1 ratio to 2 treatment arms. In addition to safety and efficacy, pharmacokinetics, and biomarkers will also be assessed.

An internal Janssen Data Monitoring Committee (DMC), independent of the study team, will be established to review the efficacy and safety data in the randomization phase. The DMC will review the totality of data after approximately 40, 60, and 90 subjects have been enrolled, including activity within distinct PD-L1 expression subgroups. Based on these findings, the DMC may formulate recommendations on study conduct, including the expansion of enrollment of some PD-L1 subgroups, resulting in greater than 96 subjects. The DMC may request additional ad hoc reviews as data accumulate.

Beginning with the implementation of Amendment 7, the Sponsor will continue to supply atezolizumab to active subjects who are deriving clinical benefit from atezolizumab monotherapy, but do not have access to commercial atezolizumab. The administration of atezolizumab will occur under the supervision of treating investigators in accordance with local regulatory approvals and standard of care guidelines.^{50,51} Data from efficacy and safety evaluations performed according to local regulatory approvals and standard of care guidelines^{50,51} will no longer be collected with the exception of serious adverse events that are to be reported and entered in the Sponsor safety repository.

Safety Run-in Phase

A 6-subject Safety Run-in cohort will be evaluated by the Safety Evaluation Team (SET; see Section 3.2) to determine the safety and tolerability of atezolizumab administered in combination with daratumumab before proceeding with the randomized phase of the study.

- Enrollment into the safety run-in will be staggered, with at least 48 hours between initiation of daratumumab + atezolizumab combination therapy (Cycle 1 Day 1) of individual subjects.
- Daratumumab will be administered intravenously (IV) at 16 mg/kg weekly on Days 1, 8, and 15, for the first 3 cycles, then on Day 1 of each 21-day cycle thereafter. Atezolizumab will be administered at 1,200 mg IV on Day 2 of Cycle 1 and on Day 1 of every 21-day cycle thereafter.
- After Cycle 1, subjects in the Safety Run-in cohort may continue to receive additional cycles of daratumumab + atezolizumab while enrollment into the Safety Run-in cohort is ongoing and after the study has proceeded to the randomization phase until they meet protocol-specified discontinuation criteria.
- If <2 of the first 6 subjects experience a dose-limiting toxicity (DLT; see Section 3.2) during the first treatment cycle (ie, 21 days), the selected doses and dose regimens for

daratumumab + atezolizumab combination therapy will be considered tolerable in subjects with advanced or metastatic NSCLC, and the study will proceed to the randomized phase after the SET provides approval.

- If ≥ 2 subjects experience a DLT, new subject enrollment into the Safety Run-in cohort will stop until after the SET convenes to review DLT data from those subjects and makes recommendations regarding the conduct of the study. The SET may consider the exploration of alternate doses and dose regimens. While the SET is reviewing the DLT data, remaining subjects in the Safety Run-in cohort who have not experienced a DLT may continue to receive additional cycles of daratumumab + atezolizumab after consultation with the Sponsor.

Randomized Phase

Approximately 90 subjects were to have been stratified based on PD-L1 expression status (IC0 and TC0 vs. others), histology (squamous vs. non-squamous), and number of previous lines of therapy (1 or >1), and then assigned randomly in a 1:1 ratio into 2 treatment arms as follows:

Arm A: atezolizumab

Arm B: atezolizumab + daratumumab IV

Treatment

Note: subjects will only be eligible to receive atezolizumab monotherapy (per Amendment 6), see Section 3.2.

For Arm A, atezolizumab will be administered at 1,200 mg IV on Day 1 of every 21-day cycle. Subjects in Arm A who experience confirmed disease progression based on RECIST 1.1 will be eligible to crossover to Arm B provided crossover eligibility criteria are met.

For Arm B, daratumumab will be administered intravenously (IV) at 16 mg/kg weekly on Days 1, 8, and 15, for the first 3 cycles, then on Day 1 of each 21-day cycle thereafter. Atezolizumab will be administered at 1,200 mg IV on Day 2 of Cycle 1 only and then on Day 1 of every 21-day cycle thereafter. Measures to prevent infusion-related reactions will include preinfusion medication (see Section 6.3). Subjects will be monitored closely for immune-mediated adverse events including pneumonitis, enterocolitis, hepatitis, dermatitis, neuropathies, and endocrinopathies.

Study visits for subjects receiving daratumumab (Safety Run-in and Arm B) will occur weekly during the first 3 cycles and every 3 weeks for all cycles thereafter. Study visits for subjects randomized to Arm A (atezolizumab alone) will occur weekly during the first 2 cycles and every 3 weeks thereafter. Subjects will continue on the assigned study treatment (atezolizumab alone or atezolizumab + daratumumab) until treatment discontinuation due to disease progression, unacceptable toxicity, or other protocol-defined treatment discontinuation criteria (see Section 10.2); or until subjects in Arm A crossover. Subjects in Arm B, who experience unacceptable toxicity directly attributable to one agent and who are experiencing clinical benefit (ie, stable disease or better) may stay on the other agent until treatment discontinuation criteria

[figure not shown]
are met, after discussion with the Sponsor. Subjects who have crossed over and experience unacceptable toxicity directly attributable to atezolizumab and who are experiencing clinical benefit (ie, stable disease or better) may stay on daratumumab until treatment discontinuation criteria are met, after discussion with the Sponsor.

Follow-up

The Follow-up phase will begin after the End-of-Treatment visit, 30 (+7) days after the discontinuation of the study drugs. Subjects will be followed for survival every 12 weeks after confirmed disease progression or start of new anticancer therapy. For subjects who discontinue treatment for reasons other than progression (eg, adverse event), disease assessments will continue to be performed until disease progression or a new cancer therapy is initiated (or another study withdrawal criterion is met, see Section 10.2).

The timing of assessments is provided in the Time and Events Schedule (Table 1). A diagram of the study design is provided in Figure 1.

Figure 1: Schematic Overview of the Study

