6.1.2 Daratumumab Treatment Schedule and Administration	As noted in Table 1 and Table 5 (Time and Events Schedules), vital signs for subjects in the Safety Run-in and Arm B cohorts should be monitored frequently on Cycle 1 Day 1 before, during, and after the first infusion of daratumumab. For all other subsequent subsequent infusions, vital signs should be measured before the start of infusion and at the end of the infusion.
6.1.3.2 Postinfusion Medication	This text is removed as it is clarified in Table 1 and Table 4: Vital signs (temperature, blood pressure, and pulse rate) should be measured <24 hours prior to each planned dose of daratumumab, every 15 (±5) minutes during the first 2 hours of each infusion, every 60 (±10) minutes thereafter for the remainder of the infusion, and at the end of infusion.
Table 1 Time and Events Schedule – Safety Run-in and Randomized Arms	Clarified that the D8 and D15 hematology and chemistry assessments are for Cycle 1 and 2 only for Arm A and for Cycles 1-3 for the Safety Run-in and Arm B cohorts. Clarified that prior medications will be collected in addition to concomitant medications.

Table 1 Time and Events
Schedule – Safety Run-in and
Randomized Arms;
Table 4 Time and Events
Schedule – Crossover

Clarified the timing of study procedures relative to dosing: For every cycle, study procedures may occur ± 3 days of the scheduled Day 1 dose, but prior to study drug administration, in order to accommodate the schedule of the site or subject. For Cycles 1 to 3, Day 8 and Day 15, study procedures may be done ± 1 day of the scheduled dose, but prior to daratumumab administration.

There should be at least 21 days between Day 1 of every dosing cycle (except for daratumumab in Cycle 1-3).

For the Laboratory Assessments, added clarification on the timing of predose testing: After Cycle 1, predose laboratory tests can be conducted up to 72 hours prior to dosing. Laboratory test results must be reviewed by the investigator or qualified designee and found to be acceptable prior to administration of each dose of study drug.

Time and Events schedules for biomarker assessments (Table 2 [new footnotes c, d, e] and Table 5 [new]); 6.2.1.9 Systemic Immune Activation; 9.4 Biomarker Assessments; 9.4.1 Tumor Tissue Samples

For the Diagnostic Archival Tissue or Fresh Biopsy, [REDACTED]

For Cycle 3, biopsy may be collected at Cycle 3 Day 1 ± 7 days but must be done following the first tumor assessment.

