Prescreening Informed Consent	X											
Archival tumor tissue (Section 9.1.2)	X											
Informed Consent		X										
Eligibility Criteria			X									
Demographics			X									
Medical and cancer history			X		4							
Tumor tissue specimen for PD-L1 testing (central lab)		X			X – Cycle 3 and at time of radiographic progression							
Vital signs (pulse, blood pressure, and temperature) and Weight Measured at Screening and on study drug dosing days. ^a			X	Arm A	X				X			
				Safety Run-in, Arm B	X	C1 only	X	X	X	X		
Physical exam, height Complete physical exam at Screening; height only measured at Screening. During the treatment period, perform a limited, symptom-directed examination as clinically indicated. Record new or worsened clinically significant abnormalities on the AE CRF.			X		----- X -----							

Table 1: Time and Events Schedule – Safety Run-in, Randomized Arms

Beginning with the implementation of Amendment 7, subjects who continue to derive benefit from atezolizumab treatment, may continue to receive atezolizumab under the supervision of treating investigators in accordance with local regulatory approvals and standard of care guidelines.^{50,51} Data from efficacy and safety evaluations performed according to local regulatory approvals and standard of care guidelines^{50,51} will no longer be collected with the exception of serious adverse events that are to be reported and entered in the Sponsor safety repository.

Assessments	Prescreening (optional)	Screening		Treatment Period (21-day cycles)						EOT (30 +7d after last dose)	Follow-up Period	
				Arm	Cycles 1-3				Cycle 4 and beyond		Pre-PD	Post-PD Survival
					D1 (±3)	D2	D8 (±1)	D15 (±1)				
Day	Any time prior to start of Screening	-56 to -1	-28 to -1									
ECOG performance status			X		X				X	X		
12-lead ECG The C1D1 12-lead ECG may be omitted if the Screening ECG was performed ≤7 days earlier. ECGs should be performed and interpreted locally. During the treatment period, a single 12-lead ECG will be performed predose on D1 of Cycles 1-4 and then predose, D1 of every third cycle (Cycle 7, 10, 13, etc.). Record new or worsened clinically significant abnormalities on the AE CRF.			X		X				X	X		
FEV-1 Only for subjects with known or suspected COPD; FEV1 <50% of predicted normal is excluded.			X									

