Hematology (see Section 9.7; performed by local lab)			X		X		X	X	X	X		
Chemistry (see Section 9.7; performed by local lab); see below for amylase, lipase			X		X		X	X	X	X		
HBV/HCV Serology (see Section 9.7; performed by local lab)			X									
Coagulation (see Section 9.7; performed by local lab)			X									
Thyroid function (see Section 9.7; performed by local lab) Amylase, lipase (see Section 9.7; performed by local lab) Screening, C4D1, every third cycle thereafter (ie, C7, C10, C13, etc.) and EOT			X						X	X		
Urinalysis – dipstick			X									
Pregnancy test – serum at Screening within 14 days prior to first study drug administration; serum or urine thereafter if clinically indicated			X									

Table 1: Time and Events Schedule – Safety Run-in, Randomized Arms

Beginning with the implementation of Amendment 7, subjects who continue to derive benefit from atezolizumab treatment, may continue to receive atezolizumab under the supervision of treating investigators in accordance with local regulatory approvals and standard of care guidelines.^{50,51} Data from efficacy and safety evaluations performed according to local regulatory approvals and standard of care guidelines^{50,51} will no longer be collected with the exception of serious adverse events that are to be reported and entered in the Sponsor safety repository.

Assessments	Prescreening (optional)	Screening		Treatment Period (21-day cycles)					EOT (30 +7d after last dose)	Follow-up Period	
				Arm	Cycles 1-3			Cycle 4 and beyond		Pre-PD	Post-PD Survival
					D1 (±3)	D2	D8 (±1)				
Day	Any time prior to start of Screening	-56 to -1	-28 to -1								
Blood group and type assessment and indirect antiglobulin (IAT). ABO, Rh, IAT A wallet card with subject blood type and IAT will be provided					C1D1 predose; Run-in, Arm B						
Study Drug Administration											
For subjects in the Safety Run-in and Arm B, the daratumumab infusion should precede the atezolizumab infusion on Day 1 of each cycle, starting with Cycle 2. Only one agent will be infused at a time. See the SIPPM for additional details. There should be at least 21 days between Day 1 of every dosing cycle (except for daratumumab in Cycles 1-3).											
Atezolizumab				Arm A	X				X		
				Run-in, Arm B	C2/ C3	C1 only			X		
Daratumumab IV (daratumumab will no longer be administered per Amendment 6)				Run-in, Arm B	X		X	X	X		
Ongoing Subject Review											

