6.3. Clinical Laboratory Tests

Descriptive statistics for values and changes from baseline over time for these laboratory parameters will be provided. In addition, shifts from baseline toxicity grade to worst toxicity grade during treatment will be generated.

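### Protocol Section 3.1 and Table 1 disagree on whether Arm A has laboratory draws on Days 8 and 15 of Cycle 3; if it does not, the SAP's worst-grade laboratory shift table rests on two more scheduled draws in Arm B

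*Protocol*

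**What the plan says.** Protocol Section 3.1 gives the arms different visit patterns. For atezolizumab alone: "Study visits for subjects randomized to Arm A (atezolizumab alone) will occur weekly during the first 2 cycles and every 3 weeks thereafter". For the safety run-in and Arm B, visits "will occur weekly during the first 3 cycles and every 3 weeks for all cycles thereafter". Arm A therefore has no visit between Cycle 3 Day 1 and Cycle 4 Day 1, while Arm B attends on Days 8 and 15 of Cycle 3.

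The same section refers the reader elsewhere for assessments: "The timing of assessments is provided in the Time and Events Schedule (Table 1"). In Table 1 the rows "Hematology (see Section 9.7; performed by local lab") and "Chemistry (see Section 9.7; performed by local lab); see below for amylase, lipase" are marked on Days 1, 8 and 15 of Cycles 1 to 3, from Cycle 4 on, and at end of treatment. The Arm cell is blank in both rows. By contrast, the vital signs row ("Measured at Screening and on study drug dosing days") is split, with Days 8 and 15 marked only for the run-in and Arm B.

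SAP Section 6.3 plans descriptive statistics over time and adds that "shifts from baseline toxicity grade to worst toxicity grade during treatment will be generated". SAP Section 2 presents all tables by treatment group. Neither section limits the worst grade to time points that both arms share, and neither asks for the number of draws.

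**The concern.** A worst grade is a maximum over the values observed. With equal follow-up, extra draws can raise it or leave it unchanged, but never lower it. If one arm is sampled more often, part of any excess of high grades in that arm comes from the schedule.

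Safety of the combination is a secondary objective, and the laboratory shift table will be read across the two columns even though no test is attached to it. With 44 subjects per arm at the third DMC review, a schedule artefact of one subject cannot be told from a drug effect unless the reader knows how many draws each arm had. As the documents stand, that number cannot be worked out for Arm A in Cycle 3.

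**Working it through.** The documents state no number of draws, so there is no plan figure to reproduce.

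**Step 1: count scheduled post-baseline hematology and chemistry draws through Cycle 4 Day 1.** Cycle 1 Day 1 is predose and so counts as baseline. The Cycle 1 Day 2 visit carries no laboratory mark in Table 1.

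| Reading | Arm A | Arm B |
|---|---|---|
| Draws follow Section 3.1 visits | C1D8, C1D15, C2D1, C2D8, C2D15, C3D1, C4D1 = 7 | the same plus C3D8 and C3D15 = 9 |
| Draws follow Table 1 as it reads | 9 | 9 |

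The difference is 2 draws under the first reading (9/7 = 1.29) and none under the second. From Cycle 4 the schedules coincide.

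**Step 2: size under the Section 3.1 reading.** Let *p* be the chance that one draw shows a given abnormality, identical in both arms. The documents give no value; 1% to 5% is an assumption.

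- Independent draws: P(at least one) = 1 − (1 − *p*)^*n*.
- Correlated draws: beta-binomial with within-subject correlation ρ = 0.2 (also an assumption). With *a* = *p*(1 − ρ)/ρ and *b* = (1 − *p*)(1 − ρ)/ρ, P(at least one) = 1 − ∏ (*b* + *i*)/(*a* + *b* + *i*), *i* = 0 to *n* − 1.

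| *p* | Independent, n = 7 → 9 | Rise | ρ = 0.2, n = 7 → 9 | Rise |
|---|---|---|---|---|
| 1% | 6.8% → 8.6% | 1.9 points | 4.3% → 5.0% | 0.7 points |
| 3% | 19.2% → 24.0% | 4.8 points | 12.4% → 14.3% | 1.8 points |
| 5% | 30.2% → 37.0% | 6.8 points | 20.0% → 22.8% | 2.8 points |

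At ρ = 0.2 the rise is 0.3 to 1.2 subjects among 44 (44 × 0.0067 and 44 × 0.0276), if all 44 reach Cycle 4.

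**Step 3: serial correlation and longer follow-up.** Serial laboratory values in one subject usually resemble their neighbours. A simulation took a subject who reaches Cycle 6 and has an end-of-treatment draw. It counted Cycle 1 Day 1 as well, giving 11 draws against 13, and let correlation decay with time.

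| Week-to-week correlation | *p* = 1% | *p* = 5% |
|---|---|---|
| 0.8 | 7.5% → 8.2% (0.7 points) | 28.9% → 30.7% (1.7 points) |
| 0.95 | 4.3% → 4.4% (0.2 points) | 16.7% → 17.2% (0.5 points) |

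**Step 4: who is affected.** Only subjects still on treatment at Cycle 3 Days 8 and 15 can have the extra draws. For anyone who stops earlier the difference is zero, so the figure for a whole arm is smaller than those above.

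**The case against.** The strongest reply is that Section 3.1 speaks of visits and itself sends the reader to Table 1 for assessment timing. Where Table 1 means the arms to differ, it splits the row. On that reading each arm has 9 draws and there is nothing to correct. This stands as far as it goes, but Section 3.1 still gives Arm A no visit at which the two Cycle 3 samples could be taken, so the conflict remains.

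The Amendment 2 log states: "Clarified that the D8 and D15 hematology and chemistry assessments are for Cycle 1 and 2 only for Arm A". A log describes superseded text and cannot be held against the current table. As history it makes the 7-against-9 reading plausible. It also raises the possibility that an arm note in Table 1 was lost when the PDF was read. If so, the contradiction disappears and the unequal draws become certain.

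A reader might infer that every Arm B subject has two extra draws and that the SAP table is therefore inflated against Arm B by construction. The documents do not support that. The extra draws depend on which passage sites follow and on remaining in treatment to Cycle 3. The net direction is also not fixed. Worst grade depends on time on treatment, Protocol Section 9.1.4 allows unscheduled repeat tests, and SAP Section 6 makes separate summaries of post-crossover safety data optional, so Arm A columns could gain later draws.

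A reader might also infer that the DMC's safety judgement was distorted. Nothing shows that this table fed that review, and Protocol Section 1.4 reports no unexpected toxicity imbalance.

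Two further points stand. The table is descriptive, and the artefact is small beside sampling error: at a 20% rate with 44 per arm, the standard error of a difference is √(2 × 0.2 × 0.8/44) = 8.5 points. SAP Sections 2.1 and 6.3 also already plan by-visit summaries, which allow comparison at shared visits, although for values and changes rather than worst grade.

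**Conclusion.** The inconsistency holds: Section 3.1 and Table 1, as it reads, give different answers on whether Arm A has hematology and chemistry draws on Days 8 and 15 of Cycle 3. The consequence for the analysis is conditional and modest. If Section 3.1 was followed, and follow-up was equal, the worst-grade table would tend to run about 0.7 to 2.8 points higher in Arm B for subjects reaching Cycle 4, at assumed per-draw rates of 1% to 5% and correlation 0.2. Under strong serial correlation the rise falls to about 0.2 to 0.5 points. If Table 1 was followed as it reads, the scheduled difference is zero. The per-draw rates and correlations are assumptions, and the reading of Table 1 needs checking against the original document.

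**What to change.** Reconcile Protocol Section 3.1 with Table 1 on Arm A laboratory draws at Cycle 3 Days 8 and 15, first checking the original table for an arm note.

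If Arm A had fewer draws, make three provisions in SAP Section 6.3:

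- Keep the all-values worst-grade shift table as the main display.
- Add a supplementary shift table limited to scheduled time points common to both arms, which omits Cycle 3 Days 8 and 15.
- Report the number of laboratory draws per subject by arm.

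The cost is a short SAP addition, one extra table and a count of draws. The supplementary table leaves out unscheduled, clinically prompted values in both arms, and the Arm B values from Cycle 3 Days 8 and 15. That is why it should sit beside the all-values table and not replace it.
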